Continued Anticonvulsants After Resolution of Neonatal Seizures: A Patient-Centered Comparative Effectiveness Study Last IRB approval: 04/20/2020 NCT02789176

RESEARCH STRATEGY

A. Background

Seizures affect ~16,000 newborns/year in the United States and have lasting adverse impacts on affected children and their families. About 15% of newborns with seizures die, and at least 50% of survivors have one or more long-term disability, including cerebral palsy, intellectual disability, and/or epilepsy¹. Many survivors require costly lifelong therapies, as well as social and academic support. More than 20% develop epilepsy within the first 12-18 months of life, and those with comorbid cerebral palsy are at highest risk^{2,3}. For the 1 in 26 Americans who have epilepsy, a history of neonatal seizures is a major risk factor for non-remittance (lack of complete response to medications)⁴. As such, neonatal seizures have a major impact, not only on the health of newborn infants, but also on their long-term neurological morbidity and chronic epilepsy [Criterion 1]. Despite the wide-ranging impacts of seizures in the newborn, alarmingly significant knowledge gaps persist [RQ-1]. The current management paradigm for neonatal seizures is to treat clinical events, with or without confirmation of EEG seizures, which can lead to both under- and over-treatment. Phenobarbital, the most commonly prescribed anticonvulsant, is often maintained for several months because of clinicians' and parents' concern that early discontinuation of medicine might cause seizures to recur⁵. However, continued exposure to phenobarbital is sedating, which may prolong the time it takes for a newborn to establish oral feeding, and this medicine may have deleterious long-term effects on the developing brain^{6,7}. Preliminary evidence suggests that early discontinuation of medication is not harmful, ^{5,6,8} but the optimal duration of therapy remains unknown. Parents of infants with neonatal seizures, including those involved in this proposal, highlight the lack of

certainty regarding treatment duration as a major concern.

The proposed PCORI-funded research will provide critical data, where very little currently exist, to guide key decisionmaking for clinicians and families of these highly vulnerably infants. This patient-centered approach highlights the main concerns of >150 parents who responded to our online "The question of... how long to continue phenobarbital after neonatal seizures is one that weighs heavily on families."

> - [name], Parent Partner and Pediatrics Resident

survey request for input on the most important research topics related to neonatal seizures.

No published studies examine the impact of anticonvulsant treatment on parent/family well-being. A few studies have focused on parents' experience after their infant's discharge home from the NICU⁹. Parents of preterm and term infants may experience apprehension, lack of confidence, and have a deep sense of responsibility for their infant's medical and developmental care. They are acutely aware of their infant's special needs, but seek to develop a sense of normalcy for their family and over time gain perspective about their experience. However, approximately one-third of parents will experience post-traumatic stress (PTSD) related to their child's hospitalization, and this has a negative impact on the family^{10,11}. It is unknown whether ongoing anticonvulsant treatment contributes to difficulties in parent and family functioning.

According to the FDA and NINDS, understanding the best management for neonatal seizures is a priority. In 2005 and 2007, the FDA and NINDS sponsored workshops on improving treatment of neonatal seizures. There was a consensus that "high priorities for research included investigations to understand adverse effects of [anti-seizure medications] and... to determine the relationship between efficacy for seizure suppression and long-term outcome"¹². Nearly 10 years later, the neonatal neurology community has failed to address either priority. Although the NIH is interested in neonatal seizure management, traditional research approaches have failed to answer important questions. In 2009, the NICHD funded a multi-center, randomized, double blind, placebo-controlled trial to examine the very question we pose by randomizing neonates with seizures that resolved within 7 days to receive phenobarbital or placebo for four months (PROPHENO, NCT01089504). Although adequate numbers of potential subjects were identified, a high proportion of parents at every participating center refused to consent, and the study was closed early after enrolling only 13 neonates. We conclude that another randomized trial is not feasible. Yet, a well-conceived, large-scale observational study with a

propensity score analysis strategy can provide the needed data and causal inference to answer the question of the optimal duration of medical treatment for neonatal seizures. [name] (PROPHENO's PI) is a consultant for our proposal and has endorsed the present study's scientific design. The clinical question, family centered design, and comparative effectiveness methods that we now propose are well aligned with PCORI priorities. The Neonatal Seizure Registry (PI [name]) is an established, multi-center collaborative of top pediatric hospitals from across the United States that is poised to answer the question of optimal duration of seizure medication through a comparative effectiveness study. The Neonatal Seizure Registry was established in 2012 with seed funding from the Pediatric Epilepsy Research Foundation. Unique among neonatal seizure studies, the Neonatal Seizure Registry is enrolling newborns at 7 American Children's Hospitals, all of which have the capability to perform long-term neonatal EEG monitoring and world-class pediatric neurology follow-up. The Neonatal Seizure Registry has collected data on more than 480 consecutive newborns to examine etiology and management of seizures in the immediate, neonatal period. The registry is currently not funded or structured to collect personal health information (PHI), or to follow patients prospectively for neurodevelopmental outcomes. With funding from PCORI, we will prospectively gather consent from families to allow collection of important PHI, and to initiate standardized follow up including EEG studies, neurodevelopmental evaluations, assessments for epilepsy, and measures of parent and family well-being.

Due to the dearth of evidence, substantial practice variability continues for neonatal seizures. Among 488 newborns enrolled in the *Neonatal Seizure Registry*, 364 had seizures due to an acute symptomatic cause and survived until the time of discharge. The registry data regarding phenobarbital treatment duration reflect two main clinical practices: 1) short duration (whereby medication is discontinued prior to discharge from hospital); *versus* 2) prolonged duration (whereby medication is continued at least until the first outpatient follow-up, typically at 2-4 months of age). Among the newborns enrolled in the *Neonatal Seizure Registry*, 23% had medication discontinued prior to discharge (range by site: 3-75%), while 77% continued on seizure medication. Phenobarbital was the most commonly prescribed anticonvulsant (89% of those maintained on medications). Although the *Neonatal Seizure Registry* sites are similar in patient acuity and conditions treated, the approach to neonatal seizures differs across sites and between providers at each site. In adjusted analyses that include seizure etiology, seizure burden, and maximum phenobarbital levels, *the study site was the only independent predictor of discharge to home with continued seizure medication* after resolution of acute symptomatic neonatal seizures (p<0.001). The present proposal will take advantage of this heterogeneity in practice to fill critical knowledge gaps regarding appropriate treatment duration for neonatal seizures.

B. Significance

Seizures affect ~16,000 newborns/year in the United States. Neonatal seizures can have substantial, lasting adverse impacts, not only for the affected children, but also for their parents and siblings. Seizures in neonates carry a high mortality rate, and at least 50% of survivors have one or more long-term disability, such as cerebral palsy, intellectual disability, and/or epilepsy¹ [Criterion 1]. For any major health condition, understanding the correct treatment choice and the ideal length of treatment is critical. Phenobarbital has been the mainstay of neonatal seizure treatment for decades, even though it is incompletely effective and has substantial side effects. How long to treat a baby with phenobarbital remains an open question [RQ-1], and this leads to significant practice variability⁵. This variability is clearly reflected in preliminary data from the *Neonatal Seizure Registry* – odds of discharge without medication vary substantially by study site (p<0.001). Animal models and observational studies of human neonates raise concern that ongoing seizures harm the developing brain¹³. Yet, prolonged treatment with phenobarbital may have neurodevelopmental consequences^{6,7}. Our proposal is designed to determine whether the duration of treatment has an impact on long-term neurodevelopment and the incidence of post-neonatal epilepsy for newborns with seizures. The results are expected to bring about substantial changes in clinical care, and will lead to meaningful improvements in healthcare and outcomes for newborns with acute symptomatic seizures. [Criterion 2; RQ-3]

The questions we seek to address through this proposal are highly relevant to parents [Criterion 4]. With our collaborators at *HandtoHold.org*, our Parent Partner [name] posted a survey requesting parent input regarding the impact of neonatal seizures, the effect of seizures and their treatment on families, and research

priorities for neonatal seizures. Within 7 days, 153 parents responded. On a scale of 0 to 10 (0= no impact, 10= very significant impact), parents responded that neonatal seizures had a major effect on their families (mean 7.8±3.2 out of 10) and, importantly, that medications to treat seizures were almost as impactful as the seizures themselves (rated 6.7±3.0). Of 81 parents who typed in their infants' treatments, 73 indicated their infant received phenobarbital. Parents indicated major concerns about medication side effects and worries about long term effects of medications on neurodevelopment. In free text responses, 72 provided feedback on priorities for research. Many highlighted the duration of therapy as a top priority research topic – "Does the child need to continue on meds and for how long?" "Do transient seizures... warrant the same preventative treatment?" "Are we over medicating these babies to prevent something that might never even happen?" "How fast should medicine be weaned?"

Furthermore, respondents wrote that sedating medications have an impact on the whole family. From one mother: "Luckily they took pictures before the seizure so that I was able to see her eyes, but I did not see them in person until she reopened them around 1 month..." [name], a Parent Partner who is both a pediatrician in training and the mother of an infant with neonatal seizures, wrote: "getting home and trying to get into a routine of what will become the new normal for our family was definitely important. It's hard to bond with your baby (and probably therefore hard to foster his/her development) in a NICU [neonatal intensive care unit]."

We presented the proposed study to the Patient and Family Research Council at the University of Michigan's Child Health Evaluation and Research Unit (CHEAR, www.chear.org). The council consists of patients and parents of patients with a variety of childhood conditions who review research proposals and provide feedback to investigators so that they may incorporate patient and family perspectives into their research design.

"[The proposed study] allows individual doctors and families to make individual decisions, and still lets the researchers learn the information we need."

> - Patient and Family Research Council, University of Michigan

Parents and patients were unanimous in their support of the proposed study question, design, and outcome measures. [Criterion 4]

C. Study Design or Approach

Specific Aims

Neonatal seizures that are due to brain injury (acute symptomatic seizures) are difficult to treat, harm the developing brain, and are associated with long-term neurodevelopmental disabilities, including intellectual disabilities, autism, epilepsy, and cerebral palsy¹. Although acute symptomatic seizures are self-limited in the neonatal period, ≥20% of patients will go on to develop epilepsy (the neonatal seizures resolve, but the infant develops recurrent, unprovoked seizures later in life) and the highest risk is in the first year of life. Recommendations for immediate treatment of neonatal seizures are based largely on pre-clinical studies which show that seizures are injurious to the developing brain through alterations in neurogenesis, neuronal loss, and excitability¹³⁻¹⁶. However, traditional and commonly used anticonvulsant medications, such as phenobarbital, are potentially neurotoxic¹⁷ and are associated with lower cognitive scores when used long-term^{6,7}. Despite this, phenobarbital, the most commonly prescribed first line medication¹⁸, is often administered for up to several months, even without electrographic confirmation of seizures⁵. A randomized, controlled trial to examine the risks and benefits of continued treatment with phenobarbital following resolution of acute symptomatic seizures (PROPHENO - NCT01089504) failed due to lack of enrollment. The fundamental management question of how long to treat seizures in the neonatal period remains unanswered. Thus, a large-scale observational study is urgently needed, to inform the critical decision regarding duration of treatment for acute symptomatic neonatal seizures¹⁹.

Our long-term goal is to improve neurodevelopmental outcomes following acute symptomatic seizures in newborns. The objective of this application is to examine whether the duration of treatment with phenobarbital has an impact on neurodevelopmental and epilepsy outcomes, as well as parent and family wellbeing, after neonatal seizures. Our collaborative research team has established the *Neonatal Seizure Registry* - a multi-center association of institutions across the United States - and has partnered with Parent Partners and

NICU Patient & Parent Advocacy groups to develop the patient centered questions and outcomes outlined in this application.

We will take advantage of heterogeneity of treatment duration for acute symptomatic seizures within our *Registry* to *determine the comparative effectiveness* of two common approaches to phenobarbital prescription for treatment of neonatal seizures for 300 enrolled neonates: (1) short duration of treatment (discontinuation of medication prior to discharge from hospital), and (2) prolonged duration of treatment (discontinuation of medication at the time of outpatient follow-up, after discharge from hospital). Importantly, based on specific stakeholder feedback, we will also examine parental and family well-being in both treatment plans. The central hypothesis of this application is that the duration of medical management has no impact on neurodevelopmental outcome or the development of post-neonatal epilepsy after acute symptomatic neonatal seizures (Aim 1) but is associated with NICU length of stay (Aim 2) and parent and family well-being (Aim 3).

Aim 1: To determine whether short *versus* prolonged phenobarbital treatment affects (a) neurodevelopmental outcome, and (b) incidence of epilepsy at age 24-months.

Hypothesis: There will be no differences in (a) functional developmental outcome, or (b) incidence of epilepsy between short duration phenobarbital treatment (*i.e.*, seizure medication discontinued prior to discharge home) and prolonged phenobarbital treatment (*i.e.*, medication continued until the time of the first clinical follow up appointment), and results of an electroencephalogram (EEG) during convalescence can be used to predict the risk of epilepsy.

Approach: Cohort study of 300 neonates with seizures due to acute symptomatic causes (*e.g.* hypoxic-ischemic encephalopathy [HIE], stroke, etc.), 150 who are newly enrolled and 150 who were previously enrolled into the *Neonatal Seizure Registry* at one of the established sites across the United States. We propose a propensity adjusted, non-inferiority, *comparative effectiveness study* of the longitudinal cohort enrolled using (a) the Warner Initial Developmental Evaluation of Adaptive and Functional Skills (WIDEA FS) - a simple, free, one-page assessment to determine functional outcome²⁰ - and (b) a simple questionnaire³ to define incidence and modified Engel classification²¹ to determine severity of epilepsy; all assessments at 12, 18, & 24 months of age. *Functional developmental outcome will be the primary outcome for this proposal.*

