Plan for developing a formal study protocol [RQ-2]. The co-PIs will finalize the draft of the Manual of Operations, clinical research forms, and consent forms during the first month of the study period. Site investigators from participating centers and our Parent Partners will be invited to provide feedback in writing and/or during a teleconference, and the PIs will incorporate this feedback prior to finalizing the documents. For the parent and family well-being aim (Aim 3), our co-investigator [name] will work with our Parent Partners to refine the co-developed protocol for measuring parent and family psychosocial dimensions, including administering the validated instruments at the time of initial hospital discharge and at the 12-month, 18-month, and 24-month follow-ups.

Study Procedures (Table 1). (1) Neonatal Clinical Data. Clinical and demographic data will be collected from the hospital charts during the neonatal admission (Appendix 1). (2) Follow-up Outpatient EEG. A 1-hour EEG will be obtained at 2-4 months corrected age, and two investigators who are blinded to treatment duration and outcome will score the studies according to published criteria^{24,25} (Appendix 2). (3) Follow Up. A trained member of the study team, who is blinded to treatment duration, will contact families to administer a validated follow-up instrument to measure functional developmental outcome (The Warner Initial Developmental Evaluation of Adaptive and Functional Skills (WIDEA FS)) and follow-up questionnaires to determine the rates and types of epilepsy at 12, 18, & 24 months old(Appendices 3 & 4). (4) Parent and family well-being. Validated instruments to measure selected dimensions of well-being and open-ended free-text guestions specific to the impact of anticonvulsant treatment impact on parents and families will be administered at the time of hospital discharge and concurrent with the other assessments (Appendix 5).
Table 1: Study Procedures and Measurements.

Study Measurements	Examples			
Neonatal Clinical Data (Appendix 1)				
- Demographics	Sex, birth weight, gestational age at birth, mode of delivery, etc.			
- Seizure etiology	HIE/ischemic stroke/intracranial hemorrhage/intracranial infection/other (based on chart review and neuroimaging findings)			
- Seizure characteristics	Presence and frequency of electrographic seizures, including presence of status epilepticus			

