Therefore, assessment of the incidence of epilepsy, and potential predictors of epilepsy, are priorities for this application. As part of the 12-month, 18-month, and 24-month assessments, parents of enrolled infants will be asked a series of questions designed to discern if the child has developed epilepsy, and if so, what type of epilepsy. Medical records will be reviewed in order to extract detailed data regarding epilepsy syndromes and treatments. All infants will undergo a follow-up 1-hour EEG when they are 2-4 months old. Two board-certified clinical neurophysiologists (Drs. [name] and [name]) who are blinded to the neonatal seizure treatment duration will score the EEG recordings using well-defined, standardized variables (**Appendix 2**), with differences resolved by consensus. The EEG results will be included in the statistical modeling of potential predictors of epilepsy. The study investigators who ascertain the epilepsy and EEG outcomes will be blinded to the treatment group.

b) Length of stay (Aim 2) is an important outcome for parents, clinicians and insurance providers. Said one parent: *"Every additional minute in the hospital... feels like an eternity... The sooner you get home, the better."* Preliminary data from the *Neonatal Seizure Registry* suggest a trend toward longer length of stay among newborns who were discharged home with medication (p=0.1).

c) Parent and family well-being (Aim 3, **PC-3**). Our Parent Partners selected the hospital discharge and 12, 18, and 24-month instruments during focus groups co-led by a study co-investigator who has extensive experience in parent engagement in research ([name]) and a lead Parent Partner ([name]). The Parent Partners discussed the most relevant domains of family well-being, reviewed the pertinent validated instruments (*e.g.* measures of quality of life, anxiety and depression, family coping, parent post-traumatic stress and post-traumatic growth, parenting confidence and competence, and family functioning), and then selected the most

PCORI Research Plan version 2 8/1/2016

relevant and valid measures (see **Appendix 5**). Questions specific to the impact of seizure medication on family well-being were developed together by the Parent Partners and investigators (see **Appendix 5**).

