Appendix 2: 2-4 Month Convalescent EEG Assessment

- 1) Date_____
- Subject # _____
- 3) Person completing EEG assessment ____
- Subject's chronological age at EEG (in weeks)______
- 5) Postmenstrual age at birth (in weeks)
- 6) Duration of recording (minutes):
- 7) Quality of recording: Acceptable Unable to interpret

8) **Overall interpretation of the EEG**:

- a. Normal
- b. Abnormal
 - i. Abnormal with epileptiform features
 - ii. Abnormal with NO epileptiform features
 - iii. Hypsarhythmia (_classic; or _____modified)

9) Specific elements:

- a. Waking background
 - i. Well-organized
 - ii. Disorganized
 - iii. Abnormal slowing (_____Focal slowing; _____Diffuse slowing; __both)
 - iv. Persistent hemispheric asymmetry (which side is abnormal: __Left____Right)
 - v. No wakefulness recorded
- b. Sleep background
 - i. Drowsy-yes, no
 - ii. Stage 2- yes, no
 - iii. SWS- yes, no
 - iv. Sleep spindles present and normal
 - v. Sleep spindles absent
 - vi. Sleep architecture asymmetric or otherwise abnormal
 - vii. No sleep recorded
- c. Epileptiform abnormalities
 - i. Focal sharp waves or spikes
 - 1. Yes
 - 2. No
 - ii. Multifocal sharp waves or spikes
 - 1. Yes
 - 2. No
 - iii. Generalized spike-wave discharges
 - 1. Yes
 - 2. No
 - iv. Electrodecrements
 - 1. Present
 - 2. Absent
 - v. Recorded seizure
 - 1. Yes
 - 2. No
- d. Other abnormalities (specify; e.g. excessive beta)

The Warner Initial Developmental Evaluation of Adaptive and Functional Skills

(Warner IDEA-FS TM) • Version 11 • March 1, 2005 Michael E. Msall, Nancy Lyon, Melissa Gray, Kathleen DiGaudio

>>> How often can your child do the following without help?

2 = Sometimes, infrequent

1 = Never

I. Self-Care: Feeding

- 1. Easily drinks formula or breast milk
- 2. Easily swallows baby food
- 3. Chews solid food
- 4. Finger feeds
- 5. Eats using a spoon
- 6. Drinks from cup without a lid
- 7. Eats using a fork

II. Self-Care: Dressing

- 1. Holds arms up so you can put shirt on
- 2. Removes socks
- 3. Pulls pants down
- 4. Pulls up a zipper once it is started
- 5. Puts on t-shirt
- 6. Removes all clothes

III. Self-Care: Diaper Awareness

- 1. Indicates a wet diaper
- 2. Indicates a soiled diaper
- 3. Voids into potty chair or toilet
- 4. Sits on potty chair and has bowel movement

Subtotal Self-Care Domain (max=68)

IV. Mobility

- 1. Rolls both ways
- 2. Maintains sitting without support
- 3. Crawls short distance
- 4. Walks few feet with assistance (cruises)

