Appendix 4: Seizure/Epilepsy Follow-Up Telephone Questionnaire (Aim 1b)

Date	
Subject #	Subject age
Person completing questionnaire	

- 1. Did your child have seizures as a newborn (at any time during the first 28 days of life)?
 - a. Yes
 - b. No
 - c. Don't know
- 2. If your child was treated with medicine for neonatal seizures, did he/she ever stop taking this medicine?
 - a. Yes, before we left the hospital
 - b. Yes, after we left the hospital
 - c. No
 - d. Don't know
- 3. Your child was treated in the hospital for his or her seizures. After you went home from that admission, did your child ever have more seizures?
 - a. Yes
 - b. No
 - c. Don't know

[If answer to 3. Is "No", then indicate answer "a" for question 5 and end telephone survey. If yes, then continue.]

- 4. Let's talk about the seizure that happened after you went home from the hospital. When did your child start having seizures?
 - a. Age_____ months
 - b. Don't know
- 5. How often does your child have a seizure now?
 - a. No seizures since he/she was a newborn
 - b. Seizure-free for at least 6 months (# of months seizure-free _____)
 - c. 1 12 seizures per year (Fewer than 1 seizure per month)
 - d. 1-4 seizures per month
 - e. 5-30 seizures per month
 - f. >30 seizures per month (daily seizures)
 - g. Multiple seizures a day (2 or more seizures per day)
 - h. Don't know
- 6. Has your child ever been diagnosed with infantile spasms (a particular kind of epilepsy)?
 - a. Yes
 - b. No
 - c. Don't know
- 7. Is your child taking medication for seizures now?
 - a. Yes (Name of medication(s), if known _____
 - b. No
 - c. Don't know

Epilepsy questions for medical record review:

- 1. Did the child remain seizure-free after discharge from the admission during which neonatal seizures were diagnosed?
 - a. Yes.
 - b. No. Acute symptomatic neonatal seizures stopped, but unprovoked seizures began later.
 i. Date of first unprovoked seizure:
 - c. No. Seizures persisted without a convalescent period.
 - d. Don't know.

2. Postneonatal seizure semiology:

- a. No seizures
- b. Seizure semiology:

	no	Yes, not specified	Bilateral, symmetric	Bilateral, asymmetric	Unilateral, focal	Unilateral, Hemi
Epileptic spasms						
Tonic						
Clonic						
Tonic Clonic						
Myoclonic-Tonic						
Myoclonic						
Myoclonic-Atonic						
Absence						
Atonic/Drop-attack						
Arrest/Staring/Blinking seizures						
Other Focal Motor						
Sensory/Autonomic						

- 3. Date of postneonatal epilepsy diagnosis:

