Appendix 6: Standards for Data Registries [DR-1 to DR-3]

Patient Follow-up will be at pre-specified ages as outlined in the proposal. The initial follow-up (2-4 month EEG) will be arranged at the time of enrollment for the N=150 prospectively enrolled infants. The Aim1 12-month, 18-month, and 24-month follow-up assessments for all participants will be conducted by telephone and will include:

- WIDEA FS (functional neurodevelopmental outcome, which is the primary endpoint, Appendix 3)
- Epilepsy assessment (Appendix 4)

As requested by our Parent Partner Advisory Panel, participating families may complete 12-month follow-up family wellbeing assessment for Aim 3 either by mail (paper copies of the questionnaires) or via online questionnaire administration (**Appendix 5**).

The 24-month contact is planned to be the last contact with patients and their families.

Adequacy of Follow-Up Duration: 24-month follow-up is both scientifically justified and practical. By 12 months, those with significant developmental delays can be identified using standard neurodevelopmental assessment instruments, such as the WIDEA FS. Additionally, those with the most severe forms of post-neonatal epilepsy, such as infantile spasms, typically present before the child's first birthday. Although more subtle developmental differences may emerge later, in school age children, longer follow-up is not feasible within a 3-year grant cycle. We plan to request permission from enrolled families to contact them at a later date for long-term outcome assessment, once additional funding is secured.

Retention and Expected Loss to Follow-Up: We anticipate excellent retention, since all neonates enrolled in this study will have close clinical follow-up with the study centers through a high-risk developmental follow-up program, pediatric neurology, and/or pediatric epilepsy. We have designed the protocol to avoid unnecessary travel to the study centers. The follow-up EEG will be recorded between ages 2 and 4 months, a timeframe during which typical neurology clinical assessments are scheduled. The assessments will be conducted via telephone interview (Aim 1), and online or by mail (Aim 3), rather than in-person evaluations. Despite this, we have accounted for a 15% loss to follow-up in our analysis plan.

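### The 2-4 month EEG is to be tested as a predictor of epilepsy by 24 months, with no requirement that the epilepsy begin after the EEG

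*Combined protocol and SAP*

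**What the plan says.** **Hypothesis and outcome.** Under Specific Aims, the Aim 1 hypothesis adds to the treatment comparison that "results of an electroencephalogram (EEG) during convalescence can be used to predict the risk of epilepsy". The epilepsy outcome of Aim 1 is the "incidence of epilepsy at age 24-months".

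**Timing of the EEG.** Study Procedures states: "A 1-hour EEG will be obtained at 2-4 months corrected age".

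**Who has it.** The epilepsy paragraph under Outcome selection states: "All infants will undergo a follow-up 1-hour EEG when they are 2-4 months old". Appendix 6 says that the recording "will be arranged at the time of enrollment for the N=150 prospectively enrolled infants".

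**Analysis.** The same epilepsy paragraph gives the whole plan for this hypothesis in one sentence: the EEG results go into a model of what predicts epilepsy. It names no at-risk population, no starting point for counting cases and no measure of accuracy.

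**Definitions and exclusions.** Specific Aims and Outcome selection describe epilepsy as recurrent unprovoked seizures that develop after the neonatal seizures have resolved. The only exclusion concerning epilepsy is for neonatal-onset syndromes.

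**Forms.** Appendix 2 records the infant's age in weeks at the EEG and scores, among other items, "Recorded seizure" and hypsarhythmia. In Appendix 4 the telephone questions ask about any seizure after going home. The chart review takes the "Date of first unprovoked seizure" and the date of the postneonatal epilepsy diagnosis, and has a separate answer reading "No. Seizures persisted without a convalescent period".

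**The concern.** A prediction concerns infants who do not yet have the outcome. Here the predictor is measured at 2-4 months, while cases are gathered over the whole period from discharge to 24 months. Epilepsy that begins between discharge and the EEG meets the protocol's definition, because that definition separates epilepsy from the neonatal seizures and not from the EEG. Such an infant enters the model as a case, and an abnormal EEG then counts as a successful forecast although the disease was already present.

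Two questions are merged: how well the EEG recognises epilepsy that has begun, and how well it forecasts epilepsy that has not. The Outcome selection section reports that the family research council wants early and accurate predictors of poor outcome, which is the second question. The analysis as written cannot isolate it.

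**Working it through.** **1. Is there a rule elsewhere?** The EEG sentence under Outcome selection, the Statistical analysis section, Sensitivity analyses, the subgroup list, the eligibility criteria and Appendices 2, 4 and 6 contain no landmark, no condition of being free of epilepsy at the EEG, and no separate handling of earlier onset. The plan gives no sample size or accuracy figure for this hypothesis, so there is nothing to reproduce.

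**2. How many cases could be involved?**
- From the documents: 300 infants, 150 of them prospectively enrolled; epilepsy incidence 20% (Sample Size Calculations, Aim 1b).
- Cases: 300 × 0.20 = 60 if all infants have the EEG; 150 × 0.20 = 30 if only the prospective infants do.
- Share begun by the EEG (f): not given. Specific Aims says only that risk is highest in the first year. Two assumed patterns give a range:
  - onset uniform over 24 months: 2/24 = 8% to 4/24 = 17%, or 5 to 10 of 60;
  - all onset uniform over 12 months: 2/12 = 17% to 4/12 = 33%, or 10 to 20 of 60.

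**3. What does mixing do?** Let S be EEG sensitivity for later-onset epilepsy and D its detection of epilepsy already present. Assume specificity 0.8, so the 240 unaffected infants yield 240 × 0.2 = 48 false positives. S, D and specificity are assumptions.

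- Sensitivity, all cases: P = f·D + (1 − f)·S. With the landmark: S.
- PPV, all cases: 60P / (60P + 48). With the landmark: 60(1 − f)S / (60(1 − f)S + 48).

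Worked example, S = 0.4, D = 0.9, f = 0.20: P = 0.18 + 0.32 = 0.50. PPV with all cases = 30/78 = 0.385; with the landmark = 19.2/67.2 = 0.286.

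| S | D | f | Begun by EEG (of 60) | Sensitivity: all / landmark | PPV: all / landmark |
|---|---|---|---|---|---|
| 0.4 | 0.5 | 0.20 | 12 | 0.420 / 0.400 | 0.344 / 0.286 |
| 0.4 | 0.9 | 0.20 | 12 | 0.500 / 0.400 | 0.385 / 0.286 |
| 0.4 | 1.0 | 0.33 | 20 | 0.598 / 0.400 | 0.428 / 0.251 |
| 0.6 | 0.9 | 0.10 | 6 | 0.630 / 0.600 | 0.441 / 0.403 |
| 0.6 | 0.5 | 0.20 | 12 | 0.580 / 0.600 | 0.420 / 0.375 |

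**4. Direction.**
- Sensitivity rises when D > S and falls when D < S (last row).
- PPV is higher with all cases whenever D > 0, because true positives are added and false positives are unchanged.
- Negative predictive value is not inflated. Early cases can only add false negatives. In the worked example it is 192/(192 + 30) = 0.865 with all cases and 192/(192 + 28.8) = 0.870 with the landmark.

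**The case against.** The strongest reply is that the plan is silent, not wrong. It names no at-risk set either way, plans no stated accuracy measure, and gives no count of early onsets. That stands as a limit on size. It does not remove the point: the hypothesis is about prediction, the outcome window opens before the predictor is measured, and following the text as written puts early-onset cases among the predicted ones.

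Several stronger readings are tempting, and the documents do not support them:

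- **Seizures that never stopped.** A reader might take the chart-review answer "No. Seizures persisted without a convalescent period" as proof that such infants count as predicted cases. They do not fit the stated definition, which needs the neonatal seizures to resolve first. The cases at issue are those with a later, separate onset that still precedes the EEG.
- **The EEG feeding its own outcome.** A reader might infer that the study EEG contributes to the diagnosis, because the chart is used to confirm epilepsy and the recruitment section says that the EEG could help care. That remark concerns expected consent, and epilepsy is defined by seizures, not by EEG. The EEG scorers are also blinded to outcome. A landmark would not cure this problem in any case.
- **Over-reliance on a normal EEG in guidelines.** The guideline planned under Dissemination concerns treatment duration, and negative predictive value is not inflated by the mixing.
- **Excluding infants by EEG result.** Treating a recorded seizure or hypsarhythmia as proof of earlier epilepsy, and dropping those infants, would select on the predictor. It could remove infants not yet diagnosed in whom the EEG gives the early warning sought.

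**Conclusion.** The point holds in a limited form. The EEG hypothesis is to be tested against epilepsy at any time to 24 months, and infants whose epilepsy began on or before the EEG would be counted as predicted. Apparent performance will be distorted to the extent that such infants exist. The likely direction is upwards, on the assumption that the EEG detects existing epilepsy better than later epilepsy.

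The size cannot be derived from the documents. Over the assumed ranges (f from 0.05 to 0.33, S of 0.4 or 0.6, D from 0.5 to 1.0, specificity 0.8), the change in sensitivity runs from about 3 points too low (0.567 against 0.60) to about 20 points too high (0.598 against 0.40). PPV is too high by about 1 point (0.427 against 0.416) to 18 points (0.428 against 0.251). To say that accuracy is known to be inflated, or by how much, would go beyond the evidence.

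This concerns a secondary hypothesis within Aim 1. The primary WIDEA FS outcome and the short-versus-prolonged comparison, including the epilepsy comparison in Aim 1b, do not depend on it. It is worth correcting because the better method is clear and nearly free.

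**What to change.** Add a short paragraph to the Statistical analysis section that makes the EEG-prediction analysis a landmark analysis:

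- **Landmark:** the date of the 2-4 month EEG.
- **At-risk set:** infants with no post-neonatal unprovoked seizure and no epilepsy diagnosis dated on or before the EEG.
- **Outcome:** epilepsy as the protocol defines it, with onset after the EEG and up to 24 months.
- **Already affected:** infants with onset or diagnosis on or before the EEG are reported separately, with their EEG findings. State also where infants whose seizures never stopped are placed.
- **EEG findings:** no infant leaves the main analysis because of what the EEG shows. Excluding those with a recorded seizure or hypsarhythmia on that EEG is a sensitivity analysis only.

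The text should also say whether the EEG analysis covers all 300 infants or the 150 prospective ones, since Outcome selection and Appendix 6 read differently and the expected cases differ (60 against 30 before losses).

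No new data are needed: age at EEG is on Appendix 2, and the dates of first unprovoked seizure and of diagnosis are on Appendix 4. Because age at EEG is recorded in weeks, the comparison needs a rule for onset in the same week. The cost is that a few cases leave the prediction analysis and its interval widens slightly.
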